4.2 MEDICAL HISTORY

Medical history will be coded with the Medical Dictionary for Regulatory Activities (MedDRA) Terminology. Events will be coded to System Organ Class (SOC) and preferred term (PT) using MedDRA Version 22.0 or higher. The number and percent of subjects with clinically significant medical history at screening will be summarized by SOC and PT for the safety populations.

4.3 PRIOR AND CONCOMITANT MEDICATION

Prior medications are defined as medications that started prior to the first dose of study drug. Concomitant medications are defined as medications (other than the study drug) taken on or after the first dose of the study drug during the entire study. Medications started before the first dose of study drug and continuing at the time of the first dose of study drug are considered both prior medication and concomitant medication. As for the medications that stopped with end date prior to study drug start date will be considered as prior medications. Partial dates for prior/concomitant medication will be classified based on rules in Section 2.3.4.

All investigator terms for medications recorded on the CRF will be coded using the World Health Organization (WHO) Anatomical Therapeutic Chemical (ATC) drug dictionary (WHODrug, March 2019 B3). Summaries of prior and concomitant medications will be provided by level 3 ATC classification and preferred term using frequency and percentages for the safety population. If ATC level 3 is not applicable, then the level 2 ATC will be used.

5. STUDY DRUG

5.1 TREATMENT COMPLIANCE

As for each subject, the individual compliance rate will be summarized by descriptive statistics for the safety population.

FCM Compliance = (total dose of iron administered/target dose) $\times 100$

5.2 EXTENT OF EXPOSURE

The total calculated FCM dose to be given (mg), the total dose of elemental iron administered (mg), the number of infusions and treatment duration (days) will be summarized descriptively.

6. EFFICACY ANALYSES

All primary and secondary efficacy analyses will be based on the safety population unless otherwise specified. Missing data will be imputed per Section 2.3.4 for primary and secondary efficacy endpoints (no imputation for descriptive statistical summaries). P-values to determine the mean difference between baseline and Day 35 will be reported. The mean difference and corresponding 95% confidence interval will be tabulated where appropriate.

6.1 PRIMARY EFFICACY ANALYSIS

6.1.1 Change in Hgb from baseline to Day 35

The primary efficacy endpoint is the change in Hgb from baseline to day 35. The actual value of Hgb on baseline, Day 35, and change from baseline to Day 35 will be summarized via descriptive statistics.

The change in Hgb from baseline to Day 35 will be assessed using paired t-tests (two-sided test, $\alpha=0.05$). Baseline Hgb will be defined as the last Hgb obtained before the first dose. Missing value will be imputed using LOCF as specified in Section 2.3.4.

6.2 SECONDARY EFFICACY ANALYSES

6.2.1 Change in ferritin from baseline to Day 35

The actual value of ferritin on baseline, Day 35, and change from baseline to Day 35 will be summarized via descriptive statistics.

The change in ferritin from baseline to day 35 will be assessed using paired t-tests (two-sided test, $\alpha=0.05$). Baseline ferritin will be defined as the last ferritin obtained before the first dose. Missing value will be imputed using LOCF as specified in Section 2.3.4.

6.2.2 Change in TSAT from baseline to Day 35

The actual value of TSAT on baseline, Day 35, and change from baseline to Day 35 will be summarized via descriptive statistics.

The change in TSAT from baseline to day 35 will be assessed using paired t-tests (two-sided test, $\alpha=0.05$). Baseline TSAT will be defined as the last TSAT obtained before the first dose. Missing value will be imputed using LOCF as specified in Section 2.3.4.

6.2.3 Change in Hgb, ferritin, TSAT and Reticulocyte Hemoglobin Content from baseline throughout the Study

The actual value of Hgb, ferritin, TSAT and reticulocyte hemoglobin content (CHr) on baseline, each post-baseline visit (Day 7, 14, 28 and 35), and change from baseline to each post-baseline visit will be summarized via descriptive statistics.

7. SAFETY ANALYSES

All safety analyses will be performed on the safety population. Safety assessments include:

- Extent of exposure
- Adverse events
- Laboratory assessments (hematology, iron indices, chemistry, and other)
- Vital signs

Baseline of clinical laboratory findings will be defined as the last value obtained before the first dose of study drug.

7.1 ADVERSE EVENTS

Adverse events (AEs) will be coded by System Organ Class (SOC) and Preferred Term (PT) using the Medical Dictionary for Regulatory Activities (MedDRA) dictionary. Adverse event

summaries will exclude preferred terms that describe asymptomatic serum ferritin, TSAT, and reticulocyte values (or changes). This approach is justified by the reporting of these values in efficacy summaries and is consistent with the protocol-defined reporting standards for hemoglobin/hematocrit and low iron indices. For the purposes of this study, non-serious anemia (hemoglobin or hematocrit below the normal range or worsened from baseline) or iron deficiency (iron indices below the normal range or worsened from baseline) will not be considered adverse events. Anemia or iron deficiency will be considered end points if an intervention is required.

A treatment-emergent adverse event (TEAE) is defined as an event with onset date on or after the study drug start date. Partial date TEAE classification rules refer to Section 2.3.4. Only TEAEs will be included in summary tables.

The incidence of TEAEs will be summarized as the number (percentage) of subjects with TEAEs within SOC and PT. Subjects who report the same PT on multiple occasions will be counted once for the PT: under the highest severity (severe > moderate > mild) CTCAE when summarized by severity and under the closest relationship (probably related > possibly related > unlikely related > none) to study drug when summarized by relationship. If a subject reports multiple PT for a SOC, the subject will be counted only once for that SOC. Events with unknown severity or relationship will be counted as unknown.

TEAEs will be summarized as below.

- An overview table, including number of subjects with
 - TEAEs
 - serious TEAEs
 - study drug related TEAEs
 - study drug related Serious TEAEs
 - TEAEs by severity
 - TEAEs leading to study drug discontinuation or withdrawal from study
 - TEAEs leading to death
- TEAE by SOC
- TEAE by PT
- TEAE by SOC and PT
- TEAE by SOC, PT, and Severity (CTCAE)
- Study drug related TEAEs by SOC, PT
- Serious TEAEs by SOC and PT
- Study drug related serious TEAEs by SOC and PT

- TEAEs leading to study drug discontinuation or withdrawal from study by SOC and PT
- TEAEs leading to death by SOP and PT

Unless otherwise stated, all TEAE tables will be sorted by SOC and PT in decreasing frequency of the number and percentage of subjects.

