7. ASSESSMENT OF SAFETY

7.1. Adverse Events

Any untoward medical event experienced by a participant during the course of this clinical trial, whether or not it is related to the investigational product, at any dose, is considered an adverse event (AE).

For any laboratory abnormality, the investigator will make a judgment as to its clinical significance. If the laboratory value is outside the normal limits and is felt to represent a clinically significant worsening from the baseline value, it should be considered an adverse event and should be recorded on the Adverse Events page of the electronic case report form (eCRF). If the laboratory value is outside the normal range, but not an adverse event, the investigator should comment on the findings (i.e., “not clinically significant” or “unchanged from baseline”) in the source documentation [laboratory

report]. All laboratory values at the EOS/Day 35 that have been deemed clinical significant by the Investigator should be followed until they are back into normal range.

To quantify the severity of adverse events, the National Cancer Institute (NCI)-Common Terminology Criteria for Adverse Events (CTCAE), Version 5 or higher should be used to grade all events. These criteria are provided in the procedure manual.

If a NCI-CTCAE criterion does not exist, the investigator should use Table 2 to assign the adverse event grade.

Table 2 Grading of Adverse Event Severity

Grade	Adjective	Description
1	Mild	Asymptomatic or mild symptoms; clinical or diagnostic observations only; intervention not indicated.
2	Moderate	Moderate; minimal, local or noninvasive intervention indicated; limiting age-appropriate instrumental activities of daily living (i.e., preparing meals, shopping for groceries or clothes, using the telephone, managing money, etc.)
3	Severe	Severe or medically significant but not immediately life-threatening; hospitalization or prolongation of hospitalization indicated; disabling; limiting self-care activities of daily living (i.e., bathing, dressing and undressing, feeding self, using the toilet, taking medications, and not bedridden.)
4	Life-threatening	Life-threatening consequences; urgent intervention indicated.
5	Death	Results in death due to the AE

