8.5.2. Adverse Events

Adverse events will be coded by system organ class (SOC) and preferred term (PT) using the Medical Dictionary for Regulatory Activities (MedDRA) dictionary.

The number and percent of participants who report treatment emergent AE (TEAE) will be summarized. A TEAE is an event with onset date on or after the study drug start date.

Adverse event summaries will exclude preferred terms that describe asymptomatic serum ferritin, TSAT, and reticulocyte values (or changes). This approach is justified by the reporting of these values in efficacy summaries and is consistent with the protocol-defined reporting standards for Hgb/hematocrit (Hct) and low iron indices. For the purposes of this study, non-serious anemia (Hgb or Hct below the normal range or worsened from baseline) or iron deficiency (iron indices below the normal range or worsened from baseline) will not be considered adverse events. Anemia or iron deficiency will be considered end points if an intervention is required.

The adverse event profile will be characterized with severity (as graded by the NCI-CTCAE) and relationship (unrelated and related) to study drug. Related adverse events will be events that are possibly or probably related to treatment in the investigator's judgment.

Participants who report the same preferred term on multiple occasions will be counted once for the preferred term: under the highest severity when summarized by severity and under the closest relationship to study drug when summarized by relationship. If a participant reports multiple preferred terms for a SOC, the subject will be counted only once for that SOC.

The number and percent of participants who report treatment-emergent serious adverse events will be similarly summarized for each treatment group. The number and percent of participants who report treatment-emergent adverse events resulting in discontinuation of study drug will be similarly summarized for each treatment group.

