7.2 CLINICAL LABORATORY PARAMETERS

Laboratory assessments include hematology, clinical chemistry, and iron indices:

- Hematology: Hgb, Hct, RBC, WBC, MCV, MCH, MCHC, RDW, platelets, differential

count, reticulocyte count and CHr

- Clinical chemistry: sodium, potassium, chloride, BUN, creatinine, albumin, alkaline phosphatase, total bilirubin, GGT, AST, ALT, LDH, calcium, phosphorus, glucose, bicarbonate and magnesium.
- Iron indices: serum iron, serum ferritin, and total iron binding capacity (TIBC), and percentage serum transferrin saturation (TSAT).
- Other: Serum pregnancy test

All laboratory parameters will be presented in conventional units. The actual value and mean change from baseline to each scheduled visit will be summarized using descriptive statistics for each laboratory test group above.

Time course table for serum phosphate will be constructed for subjects in safety population. Descriptive statistics of days to first value of specified CTC grade and days to return to normal will be summarized. Only the subjects with a normal serum phosphate baseline value will be included in this table.

The number and percent of subjects with treatment-emergent potentially clinically significant (PCS) laboratory values after baseline will be summarized by visit. The denominator is all subjects with normal baseline and at least one post baseline assessment in the safety population and the numerator is the number of subjects with PCS (i.e., meets Grade 3 or Grade 4 AE scale defined in Division of AIDS (DAIDS) Table for Grading the Severity of Adult and Pediatric Adverse Events, Version 2.1 from March 2017 (Division of AIDS, National Institute of Allergy and Infectious Diseases, National Institutes of Health, US Department of Health and Human Services)) at any post-baseline visit.

Shift from baseline AE grade to maximum post-baseline AE grade, and shift from baseline to the last visit in terms of AE grade will be summarized, separately.

The AE grade for Chemistry and Hematology are defined in Appendix 1.1. BUN, hematocrit, bands and iron indices do not have adverse event scales available and are not evaluated separately as possible AEs.

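### AE summaries exclude asymptomatic ferritin and TSAT terms in both directions, so no planned table counts participants with a clinically significant high value.

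*SAP*

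**What the plan says.** SAP 7.1 sets the rule that adverse event "summaries will exclude preferred terms that describe asymptomatic serum ferritin, TSAT, and reticulocyte values (or changes". Protocol 8.5.2 (Administrative Change 1) has the same rule: "Adverse event summaries will exclude preferred terms that describe asymptomatic serum ferritin, TSAT, and reticulocyte values (or changes".

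Both documents give two reasons. In the SAP's words:

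- "This approach is justified by the reporting of these values in efficacy summaries"
- the rule is "consistent with the protocol-defined reporting standards for hemoglobin/hematocrit and low iron indices"

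The SAP also declares that non-serious anemia and "iron deficiency (iron indices below the normal range or worsened from baseline) will not be considered adverse events".

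On recording, Protocol 7.1 says of any laboratory abnormality: "If the laboratory value is outside the normal limits and is felt to represent a clinically significant worsening from the baseline value", then "it should be considered an adverse event and should be recorded on the Adverse Events page" of the eCRF. That instruction applies to either direction.

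On laboratory tables, SAP 7.2 says: "BUN, hematocrit, bands and iron indices do not have adverse event scales available and are not evaluated separately as possible AEs". Iron indices are still one of its safety laboratory groups, with actual values and changes summarized at each scheduled visit. SAP 2.1 specifies the statistics: n, mean, SD, median, quartiles, minimum and maximum.

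**The concern.** Excluding low iron indices and anemia from AE summaries is understandable, because they are the disease under treatment and its outcome measures. The wording goes further. It removes high ferritin and high TSAT terms too, in a study of an intravenous iron product given up to a total of 1500 mg.

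Two gaps follow:

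1. **Recorded events are removed.** An investigator may judge a high ferritin to be a clinically significant worsening and record it as an AE. If it is asymptomatic, it then leaves the overview, SOC/PT, severity, related, serious and discontinuation tables.
2. **Nothing replaces the count.** No laboratory table gives the number and percent of participants with high ferritin or TSAT.

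Safety is part of the primary objective. How many children had high iron indices after treatment is an ordinary safety question, and the planned tables do not answer it.

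**Working it through.** There is no sample size, power or event figure behind this point to reproduce; SAP 1.3.3 states that no sample size was estimated. The check is mainly a cross-reading.

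**Step 1. Does the exclusion reach high values?** Yes. The terms are defined by analyte and lack of symptoms, not by direction. The statement of what is not an AE is narrower: it covers non-serious anemia and iron deficiency. Its phrase about worsening from baseline sits inside the definition of iron deficiency, so it does not turn a high ferritin into a non-event. A high value thus remains recordable under Protocol 7.1, and the exclusion then removes it from the summaries.

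**Step 2. Do the stated reasons support excluding high values?** The precedent names hemoglobin, hematocrit and low iron indices only. The reliance on efficacy summaries has no direction, but SAP 6.2.1 to 6.2.3 provides descriptive statistics and Day 35 paired t-tests for ferritin and TSAT, with no threshold and no count.

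**Step 3. Is the count available elsewhere?**

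| Planned output | Counts asymptomatic high ferritin or TSAT? |
|---|---|
| TEAE tables (SAP 7.1) | No, excluded |
| AESI tables (SAP 7.1.1) | No, there is no iron category |
| PCS table (SAP 7.2) | No, it needs Grade 3 or 4 and iron indices have no grade |
| Grade shift tables (SAP 7.2) | No, same reason |
| By-visit laboratory and efficacy statistics | Values shown, not counted |
| Listings (SAP 2.1) | Possibly, as individual records |

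**Step 4. Can the count be read from the by-visit statistics?** Only within bounds. Assume 36 participants (the planned maximum), all measured, with distinct values. Then 9 lie above Q3 and 18 above the median.

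- Limit at or above the maximum: 0 exceed it.
- Limit between Q3 and the maximum: 1 to 9 exceed it, that is 1/36 = 2.8% to 9/36 = 25%.
- Limit between the median and Q3: 9 to 18 exceed it, that is 25% to 18/36 = 50%.

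The number ever above the limit is less certain still. SAP 6.2.3 lists four post-baseline visits. If 9 exceed the limit at each visit, the number ever above it lies between 9 (the same children each time) and 4 × 9 = 36 (different children each time). SAP 2.3.3 also restricts by-visit summaries to scheduled visits, so a high unscheduled value would not appear in them.

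**Step 5. How many AEs might be dropped?** The documents give no rate. Under assumed rates p of a clinically significant, asymptomatic high ferritin or TSAT, the expected number is 36p and the probability of at least one is 1 − (1 − p)^36:

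| Assumed p | Expected participants | Probability of at least one |
|---|---|---|
| 5% | 1.8 | 0.842 |
| 10% | 3.6 | 0.977 |
| 25% | 9.0 | >0.999 |

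Under each assumption, the AE, AESI, PCS and shift tables would count none of them from ferritin or TSAT terms.

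**The case against.** The rule is prespecified and appears in both documents, so it is neither hidden nor a SAP departure. Its first reason, reporting in efficacy summaries, has no direction, and it would be wrong to say that the rationale concerns low values alone. SAP 7.2 also explains why iron indices are not graded: no scale is available. Change in ferritin and TSAT is a secondary efficacy endpoint, so a rise is the measured response. The documents nowhere name high ferritin or TSAT as a risk of the drug; the exclusion criterion on iron overload concerns history before entry.

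All of this stands. It answers the charge of concealment but not the missing count. Reporting a mean rise as efficacy does not say how many children exceeded a limit, and having no grading scale does not prevent a count against an upper limit.

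A reader might go further and infer that excess iron appears in no safety table, or that the report can say nothing about high values. The documents do not support that. Ferritin, TSAT and serum iron are in the safety laboratory tables at every scheduled visit with quartiles and maximum, which bound the proportion. Terms for serum iron or iron overload, and any symptomatic event, are not excluded by the wording. The rule restricts summaries only: eCRF recording, SAE reporting and listings are unaffected.

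A reader might also cite SAP 2.3.4, where the worst ferritin or TSAT is the lowest. That is an imputation rule for the paired t-tests when no post-baseline value exists, and it has no bearing on safety tables.

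**Conclusion.** The point holds as a gap in safety reporting. Followed as written, the plan removes recorded AEs for asymptomatic high ferritin or TSAT from every AE table, including any judged clinically significant, and no other planned table gives the number of participants affected. What is missing is the count and percentage, not all sight of the values.

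The size cannot be established from the documents. Each affected child would be 2.8% of 36, and the rates used in the working are assumptions. The conclusion rests on reading the exclusion literally, without direction, and on the SAP's statement that iron indices are ungraded. No p-value, confidence interval, alpha or sample size is affected.

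**What to change.** 1. In SAP 7.1 and Protocol 8.5.2, limit the exclusion to terms for low or decreased ferritin, TSAT and reticulocyte values. High-value events that the investigator judged clinically significant then stay in the summaries.
2. In SAP 7.2, add the number and percent of participants with post-baseline ferritin or TSAT above the central-laboratory upper limit, by visit and overall. Restrict the denominator to participants not above that limit at baseline, or present a shift from baseline. This is needed because entry allows ferritin up to 300 ng/mL, so some participants might already be above the limit. State whether the overall count includes unscheduled values.

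The documents print no upper limits for ferritin or TSAT. SAP Appendix 1.1 already takes reference limits for other analytes from the central laboratory's manual, and the same source could be used.

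The cost is one limiting phrase in each document and one small table. Protocol 9.8.5 allows changes in statistical methods to be documented by numbered memo or plan, and SAP 9 already lists such changes. The downside is that some expected, transient high values will appear in the tables; in the AE tables they are limited to those that investigators recorded as clinically significant.

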7.1.1 Adverse Events of Special Interest

Adverse events of special interest include hypophosphatemia, hypersensitivity/anaphylactoid reactions, injection/infusion site reactions, and cardiovascular events. The search strategy will be identified as follows:

- TEAEs of hypophosphatemia:
 - MedDRA PT Blood phosphorus decrease
 - MedDRA PT Blood phosphorus abnormal
 - MedDRA PT Hypophosphataemia
 - MedDRA PT Hypophosphataemic rickets
 - MedDRA PT Rickets familial hypophosphataemic
- TEAEs indicative of hypersensitivity/anaphylactoid reactions:
 - SMQ Anaphylactic reaction
 - SMQ Angioedema
 - PT Hypersensitivity
- TEAEs of injection/infusion site reactions:
 - MedDRA HLT Infusion site reactions
 - MedDRA HLT Injection site reactions
 - MedDRA HLT Administration site reactions NEC
 - MedDRA PT Infusion related reaction
- Cardiovascular TEAEs:
 - Cardiovascular disorders SOC
 - Vascular disorders SOC

The AEs of special interest will be summarized as below:

- Treatment-emergent AESI by SOC and PT
- Serious treatment-emergent AESI by SOC, PT
- Serious or severe treatment-emergent AESI by SOC and PT

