8.5.3. Adverse Events of Special Interest

Adverse events (AEs) of special interest include hypersensitivity, hypersensitivity-like reactions, and cardiovascular events. Hypersensitivity and hypersensitivity-like reactions will be identified using standardized MedDRA queries. Cardiovascular events will be identified using the SOCs for cardiac disorders and vascular disorders.

The overviews and summaries that are provided for all TEAEs will also be provided for the AEs of special interest. In addition, the time to onset and time to recovery will be summarized.

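### The hypophosphatemia AESI counts only events that investigators chose to report, and no planned table gives the incidence of low measured phosphate across all treated children

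*SAP*

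**What the plan says.** SAP 7.1.1 opens with "Adverse events of special interest include hypophosphatemia, hypersensitivity/anaphylactoid reactions, injection/infusion site reactions, and cardiovascular events". Under the label "TEAEs of hypophosphatemia" it lists five MedDRA preferred terms and gives no laboratory criterion. The resulting events are tabulated as "Treatment-emergent AESI by SOC and PT", with further tables for serious events and for serious or severe events.

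Protocol 7.1 decides which laboratory values can reach those tables. "For any laboratory abnormality, the investigator will make a judgment as to its clinical significance". A value is recorded as an adverse event when it is out of range and "is felt to represent a clinically significant worsening from the baseline value, it should be considered an adverse event". For the rest, "If the laboratory value is outside the normal range, but not an adverse event, the investigator should comment on the findings", and that comment goes into source documents. No numeric threshold is set.

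The protocol's own list (8.5.3) reads "Adverse events (AEs) of special interest include hypersensitivity, hypersensitivity-like reactions, and cardiovascular events". Hypophosphatemia is not on it, and SAP section 9 does not mention the addition among its major changes.

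Phosphorus is in the central chemistry panel (Protocol 6.4; SAP 7.2). The schedule of activities has chemistry drawn at screening and on Days 0, 7, 14, 28 and 35. SAP 7.2 plans by-visit values and changes, a serum phosphate time-course table, a Grade 3/4 (PCS) table and grade-shift tables.

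**The concern.** The SAP names hypophosphatemia as a harm of special interest, and the trial has an objective central-laboratory measurement of it at every visit. Yet the percentage shown under the AESI heading does not use that measurement. A child whose phosphate falls below the limit, and whose investigator considers the fall unimportant, leaves a note in the source record and no preferred term to count.

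At stake is the reading of a low or zero AESI figure. In a single-arm study there is no comparator recorded under the same practice, so a low figure could mean that phosphate seldom fell, or that it fell and was seldom recorded. The AESI table cannot separate the two. The question is then whether another planned table can.

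**Working it through.** **Step 1. What enters the AESI count.** SAP 7.1.1 needs a reported event coded to one of five terms. For a low phosphate value, Protocol 7.1 makes the event conditional on two things together: out of range, and judged a clinically significant worsening. The count is therefore occurrence filtered by judgement.

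**Step 2. What phosphate data exist.** Six scheduled samples per child, four of them after the first dose (Days 7, 14, 28, 35).

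**Step 3. Whether SAP 7.2 supplies the missing incidence.**

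| Planned output | Does it count children with low phosphate among all treated? |
|---|---|
| By-visit values and change | No. Means, quartiles and minima show that low values occurred, not how many children had one at any visit |
| Phosphate time course | No. Normal-baseline children only; gives times to a CTC grade that is not named and times back to normal; no incidence is listed |
| PCS table | No. Grade 3 or 4 only, and normal-baseline children only |
| Grade shifts | Not as written. Chemistry grades are said to be in Appendix 1.1, whose chemistry table has no phosphate row |

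Phosphorus is also not among the tests that 7.2 names as lacking a scale. The time-course table refers to a CTC grade, although SAP section 9 replaces CTCAE with DAIDS for laboratory values. None of these outputs is linked to 7.1.1.

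**Step 4. Size.** The documents contain no phosphate rate, no recording rate and no AESI rate, so there is no plan figure to reproduce. The following is illustration under assumptions.

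Inputs: N = 36 (the approximate maximum in SAP 1.3.3); p = assumed share of children with low post-dose phosphate; r = assumed probability that such a child has it recorded as an adverse event.

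Expected AESI count = N × p × r; expected rate = p × r.

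| p | r = 0.10 | r = 0.25 | r = 0.50 | r = 1.00 |
|---|---|---|---|---|
| 10% | 0.4 (1.0%) | 0.9 (2.5%) | 1.8 (5.0%) | 3.6 (10.0%) |
| 25% | 0.9 (2.5%) | 2.25 (6.25%) | 4.5 (12.5%) | 9.0 (25.0%) |
| 50% | 1.8 (5.0%) | 4.5 (12.5%) | 9.0 (25.0%) | 18.0 (50.0%) |

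Probability of an AESI count of zero, with children independent: (1 − p × r)^36. At p = 25%, r = 0.10 this is (1 − 0.025)^36 = 0.40, although 36 × 0.25 = 9 children would be expected to have the abnormality. At r = 0.10 it is 0.70 for p = 10% and 0.16 for p = 50%. An observed laboratory count of 9/36 would carry an exact 95% interval of 12.1% to 42.2%.

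The ratio of AESI rate to laboratory rate is simply r. The table shows how far the answer depends on an unknown quantity; it is not evidence that r is low.

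**The case against.** The strongest reply is that this is a coherent two-track design. An AESI is a subset of adverse events, Protocol 7.1 defines when a laboratory value is one, and measured phosphate is handled separately in SAP 7.2. SAP 7.1.1 never claims to estimate biochemical incidence, so the term-based count is not wrong for what it is. This stands, and it is why the AESI definition should be left alone: folding in every low value would label as AESIs results that Protocol 7.1 says are not adverse events. What the reply does not do is produce a laboratory incidence for all treated children, because the second track as written does not contain one (Step 3).

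A reader might draw stronger conclusions, which the documents do not support:

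- *Measured phosphate goes unanalysed.* It does not; 7.2 gives it a dedicated table, and the number of children contributing to the time-to-grade statistic could serve as an indirect count within the normal-baseline group once a grade is fixed.
- *The AESI rate reflects reporting habit and not phosphate.* It reflects both. With complete recording there is no shortfall.
- *Sites had no reason to report a low phosphate.* Hypophosphatemia is missing from the protocol's AESI list, but Protocol 6.4 sends laboratory results to the physician, and 7.1 requires a judgement on every abnormality.
- *Under-recording differs between the roughly 25 sites.* Possible, but nothing in the documents shows it.

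A smaller matter is the preferred term *Blood phosphorus abnormal*, which has no direction, so a high value coded there would count. Tabulation by preferred term puts it on its own row, which limits the harm.

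**Conclusion.** The point holds as a gap in reporting. The AESI percentage measures investigator-recognised hypophosphatemia and can fall below the biochemical incidence, and no planned table states that incidence for all treated children. The size of the difference cannot be estimated from the documents: anything from none (r = 1) to most of the cases is compatible with them, and the illustrative 2.5% to 25% rests entirely on the assumed p = 25% and r between 0.10 and 1. The primary endpoint is unaffected. It is worth correcting because the harm is one the SAP itself singles out and the data will already be in hand. The term-based AESI remains valid as a count of reported events; the documents do not support calling it an error or requiring its redefinition.

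**What to change.** In SAP 7.1.1, with a cross-reference to 7.2:

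1. Keep the five-term AESI unchanged and label it as reported events.
2. Beside it, give the number and percent of safety-population children with any central-laboratory phosphate after the first dose that is both below the central laboratory's age-specific lower limit and below the child's own baseline. Count each child once, and show results by baseline status (normal or already low).
3. State those phosphate limits in Appendix 1.1, which currently gives none.
4. Show the overlap: children with a reported event only, a laboratory finding only, or both.
5. For any event coded *Blood phosphorus abnormal*, flag whether it matches a low value.

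The cost is SAP wording, one derivation from data already scheduled, and an added table row with its overlap breakdown. The downside is a higher displayed figure that includes asymptomatic and possibly slight falls, so the row should be labelled as a laboratory finding and not as an adverse event.
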